4.1. Included Population

The “All included patients” analysis set will be used to show demographic and other baseline characteristics.

4.2. Efficacy Populations

The “All evaluable patients for efficacy” analysis set will be used for the primary endpoint analysis of PFS3 and secondary endpoint analyses of OS, PFS and ORR.

The secondary endpoint analysis of DOR will be based on the “All responder patients”.

The “All evaluable QoL” set will be used for the secondary endpoint analysis of changes in patients QoL.

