4. PATIENTS EVALUABILITY CRITERIA

Patients with relapsed, metastatic/locally advanced CRC with any KRAS-mutation status (wild-type, mutated, or status unknown), progressing after standard treatments (fluoropyrimidine, irinotecan, and oxaliplatin).

Patients must fulfill all the eligibility criteria to be eligible to participate in the study.

The study will include the following analysis population set definitions:

- “All Included Patients” analysis set is defined as all patients recorded in the database who have been included in the trial (excluding screening failures), independently of whether they have received the study drug or not.
- “All Treated Patients” analysis set is defined as all included patients who have received at least one (complete or incomplete) dose of the study drug.
- “All Evaluable Patients for Efficacy” analysis set is defined as all eligible patients who have at least one complete treatment cycle (or two PM060184 dose administrations over two cycles) and have, at least, one disease assessment at Week 6 and another one at Week 12. In addition, any patient who presents disease progression, symptomatic deterioration due to the disease or clinical progression, dies due to malignant disease, discontinues treatment due to unmanageable toxicity, or dies or discontinues treatment due to a treatment-related AE before evaluation of the response at Week 12 will also be considered evaluable for the primary endpoint and classified as a non-responder. Patients who have no disease assessment at Week 6 but remain on treatment and are assessed at Week 12 (or later, and with no evidence of disease progression) will be considered evaluable for efficacy. Patients who refuse further treatment before Week 12 due to reasons other than related AEs not considered unmanageable toxicity will be replaced.

- “All Responder Patients” analysis set is defined as all evaluable patients for efficacy who have had CR or PR as overall best response according to the RECIST v.1.1.
- “All Evaluable Quality of Life (QoL)” analysis set is defined as all patients who have fulfilled the EORTC-QLQ-C30 and EORTC-QLQ-CPIN20 questionnaires for at least two timepoints, one at baseline and at least one after the start of the therapy.

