Patients must be replaced if they are considered not evaluable for efficacy for the primary endpoint (PFS3), i.e., if they are withdrawn from the study due to significant clinical deterioration of unknown reason, hypersensitivity reactions, unrelated AEs without any tumor assessments after the start of study treatment, if they refuse further treatment before Week 12 due to reasons other than related AEs not considered unmanageable toxicity, if they receive less than one complete treatment cycle (at least two PM060184 dose administrations over two cycles unless treatment discontinuation was due to unmanageable toxicity), or do not have the disease assessment at Week 12 (except in the cases outlined above).

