6.2.2. Secondary Endpoints

Time-to-event variables (DOR, PFS and OS) and their fixed time estimates will be analyzed according to the Kaplan-Meier method. Kaplan-Meier curves will be plotted.

For categorical variables, comparisons will be carried out by a Fisher exact test and a multivariate analysis by logistic regression. For time-to-event variables, comparisons will be carried out by a log-rank test and by a Cox regression analysis. No formal conclusions will be expected on these grounds. Exploratory comparisons will be performed at a 0.05 level.

If appropriate, exploratory multivariate models (main effects or including interaction terms) will include all prognostic factors/covariates widely reported and recognized by oncologists: age, age at diagnosis, baseline ECOG PS (Eastern Cooperative Oncology Group Performance Status), stage at diagnosis, Tumor primary location: right vs left side tumors; sites of metastasis; visceral vs non visceral, body mass index (BMI), body surface area (BSA), time from diagnosis to first infusion, time from diagnostic of metastatic disease to first infusion, prior advanced treatment lines, last prior therapy PFS, prior oxaliplatin exposure, KRAS status, BRAF-like expression, any relevant concomitant medication at baseline; EORTC-QLQ-C30 and QLQ-CPN20 score at baseline and other prognostic/predictive factors determined by the oncologist. The total number of variables included in the final model will always be in accordance with the number of events and the sample size, thus, whenever possible, no more than one variable per ten events will be included. The parameter estimates, hazard ratios and p-values of the variables retained in the model will be presented.

A sensitivity analysis for PFS including all treated patients will be performed. Event will be defined as progression or death irrespective of the subsequent therapies received for this analysis.

Waterfall plots will be used to describe the best variation of the sum of target lesions during treatment. Questionnaires scores over time will be described by time series charts, if appropriate.

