11.3. Efficacy Analysis

Efficacy analysis will be carried out on the “All Evaluable Patients” population except duration of response analysis which will be carried out on the “All Responding Patients” population and QoL analysis, which will be carried out on the “All evaluable QoL” population.

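### OS and response rate are analysed only in the PFS3-evaluable set, with no clearly stated all-treated sensitivity analysis like the one planned for PFS

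*SAP*

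**What the plan says.** SAP 4.2 assigns one population to four endpoints: the evaluable-for-efficacy "analysis set will be used for the primary endpoint analysis of PFS3 and secondary endpoint analyses of OS, PFS and ORR". SAP 11.3 repeats this, placing efficacy on the All Evaluable Patients "population except duration of response analysis which will be carried out on the" responders, with a separate set for quality of life.

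SAP section 4 defines the evaluable set. Patients must be eligible, have received one full cycle (or two doses over two cycles), and "have, at least, one disease assessment at Week 6 and another one at Week 12". A patient with no Week 6 scan is kept if still on treatment and scanned at Week 12 or later without progression. Patients who fail early in listed ways (progression, disease-related deterioration, death from malignancy, unmanageable toxicity, death or discontinuation from a treatment-related event) "will also be considered evaluable for the primary endpoint and classified as a non-responder".

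The replacement paragraph of section 4 lists those who are not evaluable. Patients are replaced "if they are withdrawn from the study due to significant clinical deterioration of unknown reason, hypersensitivity reactions", unrelated adverse events with no tumor assessment on study, certain refusals, or too little treatment. The list closes with "or do not have the disease assessment at Week 12 (except in the cases outlined above". The responder set used for DOR "is defined as all evaluable patients for efficacy who have had CR or PR as overall best response", so it inherits the same filter.

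For PFS, SAP 6.2.2 adds: "A sensitivity analysis for PFS including all treated patients will be performed". Table 11.3.7 reports it. OS (Table 11.3.3) and ORR (Table 11.3.10) have no counterpart. Protocol 9.5 names no population for either endpoint.

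**The concern.** OS runs from the first day of treatment to death or last contact and needs no Week 12 scan. A treated patient who dies at Week 5 of an unlisted cause has a fully observed OS event, yet is left out. A patient with none of the listed failures has to reach a later assessment to be counted at all, so the set is selected on the future.

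ORR has a similar problem. A treated patient who leaves without a scan would ordinarily count as a non-responder but drops out of the denominator. A patient with a Week 6 response who leaves for an unlisted reason is lost from the numerator, and from DOR too. SAP 8.13 does not help, because it simply leaves missing values out of calculations.

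What is at stake is whether a reader of the secondary results can see how far this selection moved them. For PFS they can.

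**Working it through.** **1. The plan's own figure.** Inputs from SAP 5.1: null rate 0.30, alternative 0.50, one-sided alpha 0.025, power 90%, test variance under the null.

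- n = (1.960 × √0.21 + 1.2816 × √0.25)² / 0.20² = (0.898 + 0.641)² / 0.04 = 59.2, rounded up to 60.
- Boundary = 60 × (0.30 + 1.960 × √(0.21/60)) = 24.96, so 25.

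Both reproduce under the normal approximation. They concern PFS3 in evaluable patients only, and nothing below changes them.

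**2. Who is in the OS and ORR analyses (SAP section 4).**

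| Treated patient who, before Week 12, ... | In the set? |
|---|---|
| progresses, dies of malignancy, or stops or dies from a treatment-related event | Yes |
| dies of a cause neither malignant nor treatment-related | No |
| is withdrawn after unexplained deterioration | No |
| refuses further treatment for the reasons that lead to replacement | No |
| has no Week 12 scan and no listed exception | No |
| stops for hypersensitivity | Unclear |

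The last row is unclear because the replacement paragraph removes hypersensitivity withdrawals, while the set definition keeps anyone who stops for a treatment-related event. Protocol 6.3.2 also places severe hypersensitivity under unacceptable toxicity. Short follow-up alone does not remove a patient: SAP 11.3.1 counts evaluable patients not followed for 12 weeks as PFS3 failures.

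**3. Whether the data would exist.** The protocol follows patients for efficacy whatever the reason for stopping treatment (Schedule of Assessments, footnote 2). Follow-up ends on refusal or withdrawal of consent (6.2, 6.3.3), and survival follow-up is completed only if stage 2 opens (7.6).

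**4. Illustrative size.** No non-evaluable rate is given, so every input here is an assumption. Let f be the fraction of treated patients dropped, and Se and Sd the 12-month OS of evaluable and dropped patients. Evaluable minus all-treated OS = f × (Se − Sd). Take f = 5 to 15% and Se = 30 to 50%.

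- Sd half of Se: from 0.05 × (30 − 15) = +0.75 to 0.15 × (50 − 25) = +3.75 points.
- Sd equal to Se: 0.
- Sd 25% better: from 0.05 × (30 − 37.5) = −0.38 to 0.15 × (50 − 62.5) = −1.88 points.

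Now mix the two: a share a of dropped patients die early and the rest do 25% better, so Sd = (1 − a) × 1.25 × Se. The shift is zero at a = 1 − 1/1.25 = 20%. With f = 10% and Se = 40%, it is −1.0 point at a = 0, 0 at a = 20%, and 0.10 × (40 − 25) = +1.5 at a = 50%.

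For comparison, the 95% half-width for a 40% rate at n = 60 is 1.96 × √(0.24/60) = 12.4 points.

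For ORR, 60 evaluable patients imply 60/0.95, 60/0.90 or 60/0.85 treated, that is 64, 67 or 71 after rounding up. Suppose 6/60 = 10.0% (exact 95% CI 3.8 to 20.5%).

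- No dropped patient responded: 6/64 = 9.4%, 6/67 = 9.0%, 6/71 = 8.5%.
- One did: 7/64 = 10.9%, 7/67 = 10.4%, 7/71 = 9.9%.

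**The case against.** The strongest reply is that this is a reporting refinement. OS and ORR are secondary and SAP 6.2.2 expects no formal conclusions from comparisons on them. Many early failures stay in the set, and every assumed shift lies well within sampling error. The OS formula also treats each dropped patient's 12-month status as known. Patients who withdraw consent would be censored early and barely move a Kaplan-Meier estimate, so the range probably overstates the shift. All of that stands.

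Visibility is also better than it first looks. Table 10.1.1 shows treated against evaluable counts, Listings 10.1.4 and 12.3.7 show exclusions and deaths, and ICH listings 16.2.3 and 16.2.6 give exclusions and individual responses. The all-treated PFS analysis already counts deaths outside the evaluable set. This stands in part: the material allows some reconstruction, but none of it gives an OS estimate or a response rate with its interval.

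On ORR, Tables 11.3.9 and 11.3.36 contain a row for patients non-evaluable for efficacy, footnoted as treatment failures. One natural reading counts excluded patients as failures there. SAP 11.3 points the other way, and Table 11.3.10 states no all-treated denominator. So the row is an ambiguity, and one cannot flatly say that an all-treated response count is absent.

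Finally, protocol 8.1 defines evaluability for efficacy in general terms and the SAP follows it. This stands against changing the main population, which would also put OS and PFS on different sets. It does not count against a sensitivity analysis.

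**Conclusion.** The point holds as a cheap improvement. OS and ORR rest on a set selected by post-dose events, and the all-treated check planned for PFS is not clearly extended to them. The size and direction of any shift cannot be computed from the documents. It is probably small: about −1.9 to +3.8 points for 12-month OS, and around one point or less for ORR apart from −1.5 at 15% dropped with no response among them. Both ranges rest entirely on the assumed drop-out fractions, survival ratios and response count above. The 25-of-60 rule is not touched.

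Three stronger readings are tempting and not supported:

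- A reader might infer that OS and ORR are inflated. Dropping early unrelated deaths raises OS, but dropped refusers may do better, and a dropped responder would lower ORR.
- A reader might infer that hypersensitivity patients are simply deleted. SAP section 4 conflicts with itself on them.
- A reader might infer that all-treated results should replace the main estimates. Protocol 8.1 supports the evaluable set as the main one.

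**What to change.** In SAP 4.2, 6.2.2 and 11.3, add two sensitivity analyses in All Treated Patients, parallel to the PFS one:

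- OS, with deaths as events and all others censored at last contact.
- ORR, with patients lacking any post-baseline assessment counted as non-responders, and any response in a patient outside the evaluable set counted as a response.

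State which patients and which denominator the non-evaluable row covers in Tables 11.3.9 and 11.3.36. Reconcile the two statements in SAP section 4 on patients who stop for hypersensitivity, so that membership is settled before analysis. Keep the evaluable set as the main population, and leave PFS3, PFS and the decision rule as they are.

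The cost is SAP wording, copies of Tables 11.3.3 and 11.3.10, and one Kaplan-Meier plot. All Treated Patients is already defined and no new data are needed. If the trial stops at stage 1, survival follow-up is not completed and the OS version adds little; the ORR version is still useful.

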4.3. Safety Population

The safety analysis will be based on the “All treated patients” analysis set.

5. SAMPLE CONSIDERATIONS

5.1. Sample Size

The primary endpoint of this phase II study is PFS3. Patients will be treated with PM060184 to test the null hypothesis (H_0) that 30% or less patients are alive and free of progression at twelve weeks according to RECIST v.1.1 ($p \leq 0.30$) versus the alternative hypothesis (H_1) that 50% or more patients are alive and free of progression at 12 weeks according to the aforementioned criteria ($p \geq 0.50$). The variance of the standardized test is based on the null hypothesis. The type I error (alpha) associated with this one-sided test is 0.025 and the type II error (beta) is 0.1; hence, statistical power is 90%. Sixty evaluable patients are necessary to test the hypothesis. If at least 25 of 60 evaluable patients are alive and free of progression at 12 weeks then the null hypothesis can be rejected and PM060184 considered active and deserving potential development in this setting.

5.2. Early Stopping Rule for Futility

A futility analysis using O'Brien-Fleming boundaries is planned when 24 patients can be evaluated (first stage). If there are seven or more patients achieving PFS3 in the first stage then the trial will proceed to a second stage and a total of 60 patients will be recruited.

6. STATISTICAL METHODOLOGY FOR EFFICACY

Frequency tables will be performed for categorical variables, whereas continuous variables will be described by means of summary tables that will include the mean, standard deviation (StD), median, minimum, and maximum values of each variable.

For main efficacy results patients included in the first stage will be summarized together with patients included in the second stage.

6.1. Planned Analyses and Definitions

Primary endpoint

Progression-free survival rate at 12 weeks, defined as the rate estimate of the percentage of patients who are alive and progression-free at 12 weeks (~3 months) after the first treatment administration.

Secondary endpoints

The following time-related parameters will be analyzed according to available follow-up data:

- ***Overall Survival***, defined as the time from the first day of treatment to the date of death or last contact.
- ***Progression-free Survival***, defined as the time from the first day of study treatment to the day of assessment of progression, death or last tumor evaluation.
- ***Overall Response Rate***, defined as the percentage of patients with objective response (OR), either complete response or partial response according to the RECIST v.1.1.
- ***Duration of Response***, defined as the time between the date when response criteria (PR or CR, the first to be reached) are fulfilled and the first date when PD, recurrence or death is objectively documented.
- ***Profiles of peripheral neuropathy and quality of life*** as reported by patients using the EORTC QLQ-CIPN20 and QLQ-C30.

6.2. Efficacy Analysis Methods

6.2.1. Primary Endpoint

For the evaluation of the primary endpoint (PFS3), the efficacy population and the exact binomial estimator (count and percentage) including its 95% confidence interval will be used.

6.2.2. Secondary Endpoints

Time-to-event variables (DOR, PFS and OS) and their fixed time estimates will be analyzed according to the Kaplan-Meier method. Kaplan-Meier curves will be plotted.

For categorical variables, comparisons will be carried out by a Fisher exact test and a multivariate analysis by logistic regression. For time-to-event variables, comparisons will be carried out by a log-rank test and by a Cox regression analysis. No formal conclusions will be expected on these grounds. Exploratory comparisons will be performed at a 0.05 level.

If appropriate, exploratory multivariate models (main effects or including interaction terms) will include all prognostic factors/covariates widely reported and recognized by oncologists: age, age at diagnosis, baseline ECOG PS (Eastern Cooperative Oncology Group Performance Status), stage at diagnosis, Tumor primary location: right vs left side tumors; sites of metastasis; visceral vs non visceral, body mass index (BMI), body surface area (BSA), time from diagnosis to first infusion, time from diagnostic of metastatic disease to first infusion, prior advanced treatment lines, last prior therapy PFS, prior oxaliplatin exposure, KRAS status, BRAF-like expression, any relevant concomitant medication at baseline; EORTC-QLQ-C30 and QLQ-CPN20 score at baseline and other prognostic/predictive factors determined by the oncologist. The total number of variables included in the final model will always be in accordance with the number of events and the sample size, thus, whenever possible, no more than one variable per ten events will be included. The parameter estimates, hazard ratios and p-values of the variables retained in the model will be presented.

A sensitivity analysis for PFS including all treated patients will be performed. Event will be defined as progression or death irrespective of the subsequent therapies received for this analysis.

Waterfall plots will be used to describe the best variation of the sum of target lesions during treatment. Questionnaires scores over time will be described by time series charts, if appropriate.

6.2.2.1. QoL Analysis Methods

Changes in QoL will be followed using the EORTC-QLQ-C30 and EORTC-QLQ-CPIN20 questionnaires scores over time.

- **EORTC-QLQ-C30**

General QoL will be evaluated through EORTC QLQ-C30. These include 30 items, which transformation produces five functional scales, three symptom scales, a global health status / QoL scale, and six single items.

All of the scales and single-item measures range in score from 0 to 100, using the scoring procedures described in the manual (1). A high scale score represents a higher response level. Thus, a high score for a functional scale represents a high / healthy level of functioning, a high score for the global health status / QoL represents a high QoL but a high score for a symptom scale / item represents a high level of symptomatology / problems.

- **EORTC-QLQ-CIPN20**

Peripheral neuropathy will be evaluated through EORTC QLQ-CIPN20, a 20-item quality of life questionnaire for the patients' self-reported neurotoxicity, targeting symptoms and patient concerns specifically associated with treatment-induced PN and potential activity impairment.

The EORTC QLQ CIPN20 consists of three subscales: sensory scale, motor scale and autonomic scale. For all of them, the individual items and the multi-item scale should be scored such that higher scores represent more symptoms/problems (i.e., higher score = worse).

If forming a scale appears to be justified, then the same algorithm can be used as is applied in the scoring manual for the QLQ-C30 for linearly converting items and/or scales to 0-100 scales.

The module items will be reported both individually and in the form of mean scores. If item mean scores are being presented, the items should first be linearly converted to a 0 to 100 scale, whilst it will be reported the percentage of patients endorsing each of the response categories for the first case. It could be displayed by dichotomize scores also, if appropriate, for example by grouping scores into 'Not at all' vs. 'Any extent'.

Finally, QoL and PN will be evaluated by changes in the EORTC QLQ-CIPN20 and QLQ-C30 scores over time and tested for statistical significance by means of repeat-measure analyses of variance. The scores will be compared at the pre-specified time points using a T-test for related samples to establish differences, if any, between pairs of assessments. A p-value of < 0.05 is considered statistically significant for the exploratory comparisons.

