9.7 PATIENT REPORTED OUTCOMES

PRO analysis will be performed on summary measures and longitudinal modelling of patients' QLQ responses. QoL and PN will be evaluated by changes in the EORTC QLQ-CIPN20 and QLQ-C30 scores over time and tested for statistical significance by means of repeat-measure analyses of variance. The scores will be compared at the pre-specified time points using a T-test for related samples to establish differences, if any,

between pairs of assessments. A p-value of < 0.05 is considered statistically significant for the exploratory comparisons.

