8.12. Subgroup Analyses

If applicable, specific analyses for different subgroups determined by the following factors will be developed: prior oxaliplatin exposure, tumor primary location: right vs left side tumors, KRAS status, BRAF-like expression, MSI phenotype and other relevant factors determined by the oncologist.

No differentiation by center is planned.

8.13. *Methods for Handling Missing Data*

Missing values will not be included in the calculation of outputs.

8.14. *First Stage Analysis*

A futility analysis will be performed once the first 24 evaluable patients complete the Week 12 (± 5 days) tumor assessment; progress; die due to PD; or discontinue treatment due to unmanageable toxicity (whichever occurs first). If seven patients or more achieve PFS3, then 36 additional patients will be recruited (second stage).

8.15. *Identification of Fixed or Random Effects Models*

Not applicable.

8.16. *Data Analysis Conventions*

All data analysis conventions, data calculations and grouping needed to perform the statistical analysis will be described in a separate document.

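### The on-treatment CIPN20 and C30 tests rest, cycle by cycle, on patients still being treated; a mixed model would use the collected scores better, though end-of-treatment and follow-up forms soften the problem

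*SAP*

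**What the plan says.** SAP 6.2.2.1 has the scores "tested for statistical significance by means of repeat-measure analyses of variance" and compared at set time points "using a T-test for related samples to establish differences, if any, between pairs of assessments", at an exploratory 0.05 level. Protocol 9.7 gives the same two methods ("scores over time and tested for statistical significance by means of repeat-measure analyses of variance"). It opens more broadly, "PRO analysis will be performed on summary measures and longitudinal modelling", but the SAP names no model beyond the ANOVA.

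Four other places bear on this:

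- SAP 4 admits to the QoL set patients with forms "for at least two timepoints, one at baseline and at least one after the start of the therapy".
- SAP 8.13: "Missing values will not be included in the calculation of outputs". SAP 8.15, "Identification of Fixed or Random Effects Models", is answered as not applicable. SAP 8.16: "All data analysis conventions, data calculations and grouping needed to perform the statistical analysis will be described in a separate document".
- Tables 11.3.21 and 11.3.26 have columns for DF, mean square, F and p-value. Tables 11.3.20 and 11.3.25 give mean change, StD and p-value per visit, without N or confidence interval.
- Protocol 8.3 collects both questionnaires at baseline, on Day 8 of each cycle and at end of treatment (EOT). In follow-up it collects CIPN20 only, monthly for patients who stopped because of grade 3 or worse neuropathy.

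**The concern.** Day 8 forms exist only while treatment continues, so each later paired test describes a smaller and possibly selected group. The QoL set lets in patients who stop early, but the per-cycle tests make no use of their early scores when estimating later change. An ANOVA restricted to patients with every visit would go further and discard those patients altogether.

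Two things are at stake. One is precision, which is lost even if stopping has nothing to do with the scores. The other is the size of the reported worsening: if patients with more neuropathy stop sooner, the remaining patients look better than the cohort would have looked under continued treatment. Describing the neuropathy and quality-of-life profile is a secondary objective (Protocol 3), and Protocol 1.2.2 names sensory neuropathy as the main toxicity that limited dose.

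**Working it through.** **Cohort.** The documents give no effect size, SD or dropout rate for the questionnaires, so the planned 60 patients serve as the cohort. That figure reproduces: N = [1.96·√(0.3·0.7) + 1.2816·√(0.5·0.5)]² / 0.2² = 59.2, rounded up to 60.

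**Retention at Cycle 4 Day 8.** This visit is study day 3·21 + 8 = 71. Inputs are p = 0.30 and 0.50 at 84 days (SAP 5.1) and scans every six weeks (Protocol 7.4). Progression-free status stands in for being on treatment.

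- Constant hazard, 60·p^(71/84): 21.7 and 33.4.
- Stops only at the Week 6 scan, 60·√p: 32.9 and 42.4.

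Patients with a Cycle 1 Day 8 form number 60·p^(8/84) = 53.5 and 56.2 under constant hazard, and all 60 under scan-only stopping. The QoL-set patients missing from the Cycle 4 paired test are therefore 53.5 − 21.7 = 31.8, 56.2 − 33.4 = 22.8, 60 − 32.9 = 27.1 and 60 − 42.4 = 17.6, or about 18 to 32.

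**Precision when stopping is unrelated to score.** The estimates are unbiased. Simulated trials of 60 used two sets of assumed variances:

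- Set A: baseline SD 10, worsening 5 points per cycle (SD 5), residual SD 5.
- Set B: between-patient SD 12, worsening 4 points per cycle (SD 3), residual SD 7.

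| Set | Retained at Cycle 4 | SE paired | SE mixed model | Excess |
|---|---|---|---|---|
| A | 22 | 4.64 | 3.52 | 32% |
| A | 33 (constant hazard) | 3.67 | 3.10 | 18% |
| A | 33 (scan) | 3.82 | 3.01 | 27% |
| A | 42 | 3.41 | 2.97 | 15% |
| B | 22 | 3.06 | 2.76 | 11% |
| B | 34 | 2.40 | 2.20 | 9% |

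Taking all runs together, the excess is roughly 8 to 34%. If the ANOVA uses all observed forms with patient and visit effects, its Set A standard errors are 3.94, 3.33, 3.40 and 3.18, an excess of 7 to 13%.

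**Bias when some stopping follows worse scores.** The share of score-related stops is assumed; the documents do not give it. In a large simulation with Set A, and with a slower worsening of 3 points per cycle (SD 3), the score-related hazard doubled per 10 points of change. The paired estimate at Cycle 4 was 2 to 13% low at a 10% share and 5 to 27% low at a 25% share. Examples at 25%, against a true change of 20, with stopping driven by the last observed score:

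- 22 retained: paired 15.8 (21% low), mixed model 20.0.
- 33 retained (scan): paired 17.5 (12.5% low), mixed model 20.0.
- 42 retained: paired 18.6 (7% low), mixed model 20.0.

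**Limit of the model.** When stopping is driven by the unseen current score, results depend on the assumptions. In the first simulation the mixed model was 1 to 3% low at the 10% share and 2 to 8% low at 25%. Under Set B with a strong dependence it had no advantage: truth 13.3, paired 9.8 to 10.8, model 9.7 to 10.8.

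**Where the documents place the share.** Protocol 1.2.2 reports dose-limiting neuropathy in 6% of patients above the recommended dose. As an illustration only, 6% of 60 is 3.6 patients. Set against 60 − 22 = 38 or 60 − 42 = 18 stops by Cycle 4, that is 9% or 20%. This trial starts at the recommended dose, and Protocol 5.4 provides for dose reductions for neuropathy before discontinuation. Both suggest the lower part of the assumed range.

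**The case against.** The strongest reply is that early stoppers are not lost. Both questionnaires are due at EOT, Tables 11.3.20 and 11.3.25 test change at that visit, and patients who stop for severe neuropathy fill in CIPN20 monthly. This stands as real mitigation, although EOT attendance is not assured and the form comes about 30 days after the last dose, so it measures a different state from Day 8 on treatment.

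Second, the objective is descriptive, and an observed on-treatment mean is a fair description of patients still on treatment. It is low only against the course under continued treatment, which the plan does not claim to estimate. That also stands; what remains is that the plan does not say which it means.

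Third, the bias may be within noise. At a 10% share it is at most 13% of 20, or 2.6 points, against paired standard errors of 3.4 to 4.6. Under strong score-related stopping in Set B the mixed model's standard error was no smaller (2.57 against 2.53; 3.33 against 3.02), so the gain there is lower bias only.

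Fourth, a reader might infer that the ANOVA is certainly complete-case. SAP 8.13, 8.15 and the table shells make that likely, but 8.13 also fits an analysis of all observed forms, and 8.16 sends conventions to a document not provided. Likewise, missing N and confidence intervals is true only of the change tables: Tables 11.3.17 and 11.3.22 give N per item, and Figure 11.3.24 plots means with 95% intervals.

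**Conclusion.** The point holds as an improvement to consider. The per-cycle paired tests use about 22 to 42 of 60 patients at Cycle 4. They cost roughly 8 to 34% in standard error if stopping is unrelated to score. They understate worsening by roughly 2 to 27% against continued treatment if 10 to 25% of stops follow worse scores, with the low end more likely. The direction follows from which patients are used; the sizes rest on assumed SDs, linear worsening that ignores dose reductions and delays, and the assumed share.

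A reader might infer that the plan hides much of the neuropathy burden, or that half of all stops could be score-related. The documents support neither. EOT and follow-up CIPN20 are analysed, CTCAE neuropathy is reported in all treated patients, and nothing in the protocol suggests so large a share. For C30 no link between score and stopping is shown, so the case there is precision and clarity. The comparisons are exploratory and the PFS3 decision is untouched.

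**What to change.** Amend SAP 6.2.2.1 and Protocol 9.7 together:

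- Make the on-treatment analysis a likelihood-based mixed model for repeated measures on all available Day 8 scores of the QoL set. Include baseline score, categorical visit up to a named last cycle (for example Cycle 4), and unstructured covariance with a named simpler fallback such as heterogeneous Toeplitz.
- State that it assumes missing at random and targets the course under continued treatment. Keep observed on-treatment means as description.
- Keep EOT and follow-up comparisons as separate summaries; use EOT forms in the model only in a labelled sensitivity analysis.
- Add a delta-adjusted sensitivity analysis for CIPN20, since the model does not fully remove bias when stopping depends on the unseen current score.
- Add N, 95% CI and completion rate to Tables 11.3.20 and 11.3.25. Bring SAP 8.15 and Tables 11.3.21 and 11.3.26 into line.
- Remove the Follow up column from the C30 tables (11.3.17, 11.3.18, 11.3.20), because C30 is not collected then.

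The cost is wording, revised shells and a different SAS procedure; no new data are needed. The drawbacks are reliance on missing at random and few patients in late cycles across 3 CIPN20 and 15 C30 scales, hence the named last cycle and fallback.
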